1.4.1.2. Extension Phase

During the extension phase of the study, participants will receive 2550 mg CCI of both GS-5423 and GS-2872 administered IV in combination with LEN every 26 weeks. The dose selection for GS-5423 and GS-2872 in the extension phase is based on analysis of Week 52 data from the randomized phase of this study (GS-US-536-5939).

In the randomization phase, both GS-5423 and GS-2872 were evaluated at 2550 mg every 6 months, administered IV in combination with LEN. At Week 26 and Week 52, 1 and 3 participants receiving LEN, teropavimad (TAB), and znlirvimab (ZAB), respectively, had HIV-1 RNA $50 \geq$ copies/mL, and none of the participants who remained on a stable baseline regimen had HIV-1 RNA ≥ 50 copies/mL by snapshot algorithm.

Updated population pharmacokinetic (PopPK) models were developed for TAB and ZAB using data from the Phase 1b and Phase 2 (up to Week 52) studies to inform dose selection for extension phase evaluation of TAB and ZAB in combination with LEN. The PopPK model identified a statistically significant relationship between body weight and PK parameters for both TAB and ZAB, described by allometric scaling, resulting in a trend towards lower exposures in participants with higher body weight. Among the 3 participants with VF through Week 52 in the Phase 2 study, all weighed over 100 kg and generally had exposures below the median for both TAB and ZAB or LEN (Figure 2). Although the number of virologic failures through Week 52 in the Phase 2 study was limited (N = 3) and a definitive association between lower exposure and reduced efficacy cannot be established from Phase 2 Week 52 data, alternative dosing options for both TAB and ZAB to mitigate potential risk in higher-weight individuals were evaluated.

Model-based simulations of TAB and ZAB exposures (AUC , C_{max} , and C_{trough}) were conducted to assess the relationship between body weight and drug exposures, based on the body weight distribution of pooled historical Phase 3 studies in the virologically suppressed PWH population.

CCI

CCI

[figure not shown]

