3.1.3. Per Protocol Analysis Set

The Week 26 or Week 52 Per Protocol (PP) Analysis Set includes all participants in the FAS excluding participants who committed any major protocol violation, including the violation of key entry criteria.

Participants meeting any of the following criteria will be excluded from the Week 26 or Week 52 PP analysis set:

- 1) did not have on-treatment HIV-1 RNA in the Week 26 or Week 52 analysis window, except when missing is due to discontinuation of study drug for lack of efficacy as in Table 3-1.
(Note: lack of efficacy is defined as having the check-box for Lack of Efficacy marked as the reason for premature study drug discontinuation on the study drug completion eCRF page)
- 2) Received partial or missed oral LEN doses on Day 1 or Day 2.
- 3) Any prior receipt of LEN or a bNAb for HIV-1 treatment (Exclusion criteria 1)
- 4) Have been treated with immunosuppressant therapies or chemotherapeutic agents (eg, corticosteroids, immunoglobulins, and other immune- or cytokine-based therapies) within 4 weeks of study screening or have an anticipated need for such treatment during the study (Exclusion Criteria 3).

Table 3-1. Participants Excluded from Week 26 or Week 52 PP Analysis Set Due to Premature Discontinuation of Study Drug and/or Missing HIV-1 RNA Assessment in Week 26 or Week 52 Analysis Window

Discontinuation from Study Drug prior to or on the Upper Bound of Week 26 Analysis Window		HIV-1 RNA Data on Treatment Available in Week 26 or Week 52 Analysis Window	
		Yes	No
Yes	Due to Lack of Efficacy	+	+
	Due to Other Reasons	+	-
No		+	-

+ = Inclusion of Participants in Week 26 or Week 52 PP analysis set; - = Exclusion of Participants in Week 26 or Week 52 PP analysis set

The PP Analysis Sets are the secondary analysis sets for efficacy analysis.

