 - last exposure date is defined as the last dose date (randomized phase).

ART Restart Date is defined for treatment group 1 as the earliest ARV start date after permanent discontinuation of LA study regimen for participants who discontinued study drug.

Baseline Value is defined as the following by the treatment group that participants were randomized to:

- Treatment group 1: the last value obtained on or prior to the first dose of the randomized phase.
- Treatment group 3: the last value obtained on or prior to the Study Day 1 (Randomized Phase).

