6.1.2. US FDA-Defined Snapshot Algorithm

The analysis window at Week 26 is defined as from Study Day 176 to Study Day 224, inclusive for treatment group 1 and Study Day 134 to Study Day 224, inclusive for treatment group 3. All HIV-1 RNA data collected on-treatment during the randomized phase will be used in the US FDA-defined snapshot algorithm. Virologic outcome will be defined as the following categories:

- **HIV-1 RNA < 50 copies/mL:** this includes participants who have the last available on-treatment HIV-1 RNA < 50 copies/mL in the Week 26 analysis window
- **HIV-1 RNA ≥ 50 copies/mL:** this includes participants
 - a) Who have the last available on-treatment HIV-1 RNA ≥ 50 copies/mL in the Week 26 analysis window, or
 - b) Who do not have on-treatment HIV-1 RNA data in the Week 26 analysis window and
 - Who discontinue study drug prior to or in the Week 26 analysis window due to lack of efficacy, or
 - Who discontinue study drug prior to or in the Week 26 analysis window due to AE or death and have the last available on-treatment HIV-1 RNA ≥ 50 copies/mL, or
 - Who discontinue study drug prior to or in the Week 26 analysis window due to reasons other than AE, death, or lack of efficacy and have the last available on-treatment HIV-1 RNA ≥ 50 copies/mL.

- **No Virologic Data in the Week 26 Window:** this includes participants who do not have on-treatment HIV-1 RNA data in the Week 26 analysis window because of the following:
 - Discontinuation of study drug prior to or in the Week 26 analysis window due to AE or death and the last available on-treatment HIV-1 RNA < 50 copies/mL, or
 - Discontinuation of study drug prior to or in the Week 26 analysis window due to reasons other than AE, death, or lack of efficacy and the last available on-treatment HIV-1 RNA < 50 copies/mL or,
 - Missing data during the window but on study drug.

The flowchart of the US FDA-defined snapshot algorithm is provided in Appendix 2.

The Week 26 virologic outcomes for the US FDA-defined snapshot algorithm will be listed.

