6.2.2. Analysis of the Secondary Efficacy Endpoints

6.2.2.1. Analysis of the Proportion of Participants with HIV-1 RNA \geq 50 copies/mL at Week 52 as Determined by US FDA-defined Snapshot Algorithm

The proportion of participants with HIV-1 RNA \geq 50 copies/mL at Week 52 as determined by US FDA-defined snapshot algorithm will be analyzed similarly to the primary efficacy endpoint.

For both treatment group 1 and 3, the analysis window at Week 52 is defined as from Study Day 358 to Study 406 if a participant did not enter the extension phase, or to Study Day 1 (extension phase) if a patient entered the extension phase.

The analyses for the above endpoint will be conducted using the FAS and the Week 52 PP analysis set, respectively.

6.2.2.2. Analysis of the Proportion of Participants with HIV-1 RNA $<$ 50 copies/mL at Weeks 26 and 52 as Determined by US FDA-defined Snapshot Algorithm

The proportion of participants with HIV-1 RNA $<$ 50 copies/mL at Weeks 26 and 52 as determined by US FDA-defined snapshot algorithm will be analyzed similarly to the primary efficacy endpoint, and be conducted using the FAS and the PP analysis set correspondingly.

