Appendix 2. Flowchart of US FDA-defined Snapshot Algorithm (for Long Acting Switch Trial)

The following flowchart for US FDA-defined snapshot algorithm is based on the US FDA Guidance on Human Immunodeficiency Virus-1 Infection: Developing Antiretroviral Drugs for treatment {U. S. Department of Health and Human Services 2015}.

On-Treatment HIV-1 RNA data include: 1)for treatment group 1: HIV-1 RNA data collected up to the earliest date of (196 days [28 weeks] after the last dose date of complete long acting regimen, date of restarting ART); 2)for treatment group 3: HIV-1 RNA data collected up to 1 day after permanent discontinuation of study drug.

Participants with study drug premature discontinuation are defined as participants who were answered “No” to “Did subject complete study drug dosing as specified per protocol?” in Study Drug Completion eCRF).

The date of study drug premature discontinuation is

- 1) The earliest (196 days [28 weeks] after the last dose date of complete long acting regimen, ARV restart date, last study date) for participants who prematurely discontinued study drug for treatment group 1
- 2) The date of permanent discontinuation of baseline oral ART regimen for treatment group 3.

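### Table 3-1 applies the Week 26 discontinuation cut-off to the Week 52 per-protocol set, so a late stop for lack of efficacy can be excluded from it

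*SAP*

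**What the plan says.** SAP 3.1.3 defines the Week 26 and Week 52 PP sets together. Criterion 1 removes participants without on-treatment HIV-1 RNA in the relevant window, "except when missing is due to discontinuation of study drug for lack of efficacy as in Table 3-1". Lack of efficacy means that box is ticked on the study drug completion form.

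The title, data columns and footnote of Table 3-1 all name both visits. The row condition names only one: "Discontinuation from Study Drug prior to or on the Upper Bound of Week 26 Analysis Window".

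The windows are in SAP 6.1.2 ("The analysis window at Week 26 is defined as from Study Day 176 to Study Day 224, inclusive for treatment group 1") and SAP 6.2.2.1 ("the analysis window at Week 52 is defined as from Study Day 358 to Study 406", or to extension Day 1 for those who enter the extension). SAP 3.1.3 also gives the role of these sets: "The PP Analysis Sets are the secondary analysis sets for efficacy analysis". The Week 52 PP set is used for both Week 52 snapshot proportions and for change in CD4 count (SAP 6.2.2).

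**The concern.** Week 52 is the first look at efficacy over a second 26-week dosing interval. A participant who loses suppression after the Week 26 dose, develops resistance and returns to oral ART is the event it should detect. Such a participant will often have no on-treatment RNA in the Week 52 window, because on-treatment data end at ART restart (SAP 6). The lack-of-efficacy exception exists to keep these participants. If the table cancels it after Day 224, the Week 52 PP set drops them because they failed, and the PP and FAS results then differ for a reason nobody intended.

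**Working it through.** **What the header controls.** The lack-of-efficacy row includes participants with or without window RNA. The other-reasons row and the not-discontinued row are identical: included with window RNA, excluded without. The cut-off therefore matters for one combination only, a lack-of-efficacy stop with no on-treatment RNA in the window.

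| Lack-of-efficacy stop, no on-treatment Week 52 RNA | Cut-off Day 224 (as written) | Cut-off at end of Week 52 window |
|---|---|---|
| Stop by Day 224 | kept | kept |
| Stop from Day 225 to end of Week 52 window | excluded | kept |

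**Does the protocol's pathway reach that cell?** In Group 1, on-treatment data end at the earlier of 196 days after the last complete long-acting dose and ART restart (SAP 6).

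- Second dose at Day 182, visit window ±6 days: 176 + 196 = 372, 182 + 196 = 378, 188 + 196 = 384. All lie inside Days 358 to 406. Without ART restart, a Week 52 sample near Day 364 is on-treatment and the participant is kept.
- Dose 1 only: 1 + 196 = 197, before Day 224. If the stop is dated as in Appendix 2, it falls by Day 224 and the participant is kept.
- The gap therefore needs a second dose, then a stop from Day 225, and usually ART restart before Day 358. Example: rebound at Week 38 (Day 266) and a confirmatory draw 2 to 3 weeks later (Days 280 to 287; protocol 6.3.9.2.1). Resistance is found and ART is restarted on, say, Day 300 (my assumption). On-treatment data end 58 days before the window opens, so the table excludes this participant.

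**The same participant in the FAS.** SAP 6.1.2 counts a lack-of-efficacy stop without window RNA as HIV-1 RNA ≥ 50 copies/mL. SAP 6.2.2.1 carries the method to Week 52 with the Week 52 window. The FAS records a failure and the PP set has no record.

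**Possible size.** The plan gives no figure for this analysis. Protocol 1.4.1.2 reports 1 Group 1 snapshot failure at Week 26, 3 at Week 52, and none in Group 3, so at least 3 − 1 = 2 of the Week 52 failures were not Week 26 failures. Analysed denominators are not given, so I assume the planned 50 and 25. Clopper-Pearson limits are the 0.025 quantile of Beta(x, n − x + 1) and the 0.975 quantile of Beta(x + 1, n − x).

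| Failures dropped | Week 52 PP, Group 1 | 95% CI |
|---|---|---|
| 0 | 3/50 = 6.0% | 1.3 to 16.5 |
| 1 | 2/49 = 4.1% | 0.5 to 14.0 |
| 2 | 1/48 = 2.1% | 0.1 to 11.1 |

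If all three met the conditions, the result would be 0/47. With the score-based exact unconditional method and 0/25 in Group 3, the difference intervals are about −8 to 17, −11 to 14 and −12 to 12 percentage points. All include 0. The same method reproduces the plan's sample-size thresholds of 8 and 12 failures (one-sided p 0.0239; one failure fewer gives 0.0403), and this point does not affect them.

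**The case against.** The best defence is that this is one header left unadapted. Everything else in the table names both visits, criterion 1 states the intent, and a careful programmer would apply the Week 52 bound. The set is secondary, and SAP 1.3 says the study is not powered to compare treatments. All of that stands and limits the severity. It does not remove the error, because criterion 1 applies its exception only as the table sets it out.

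Table 3-1 also does not say which date counts as discontinuation. I used the Appendix 2 date: the earliest of 196 days after the last complete dose, ARV restart and last study date. If the last dose date were used (about Day 182), the participant would be kept.

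A reader might infer something stronger: that late rebounds also escape the FAS failure count. Appendix 2 says "Participants with study drug premature discontinuation are defined as participants who were answered" No to completing dosing per protocol, and SAP 3.8.1 defines ART restart as the "earliest ARV start date after permanent discontinuation of LA study regimen for participants who discontinued study drug". Someone who received both randomized-phase doses and then rebounded might be recorded as a completer, have no restart date, and be counted as suppressed once back on oral ART. The documents do not support this as a finding:

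- The form answer is unsettled. SAP 3.8.1 counts only Day 1 and Week 26 long-acting doses for the randomized phase. Protocol 6.3.11.1, however, treats a Group 1 stop before Week 52 as early discontinuation, and protocol Table 4 lists a Week 52 dose.
- SAP 6 ends on-treatment data at ART restart with no condition on that form.
- Protocol 1.4.1.2 reports 3 Week 52 snapshot failures and also refers to virologic failures with the words "Among the 3 participants with VF through Week 52 in the Phase 2 study". The counts agree, so there is no sign of a lost FAS failure.

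**Conclusion.** The point holds for the Week 52 PP set only. As written, Table 3-1 excludes lack-of-efficacy stops from Day 225 that have no on-treatment RNA in the Week 52 window, contrary to criterion 1 and to the FAS classification. The bias is toward fewer failures. Participants with on-treatment window RNA, and lack-of-efficacy stops by Day 224, are unaffected.

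The size is unknown. The fall from 6.0% to as low as 2.1% assumes the planned denominators and that up to two of the reported failures stopped for lack of efficacy after Day 224 without window RNA. The protocol gives neither the reasons for stopping nor the dates, so the number dropped could be zero. No reported result is shown to be wrong. Severity: minor to moderate.

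**What to change.** Make the Table 3-1 row condition visit-specific: discontinuation up to the upper bound of the Week 26 window for the Week 26 PP set, and up to the upper bound of the Week 52 window for the Week 52 PP set. State that the discontinuation date is the one defined in Appendix 2. Week 52 results already exist, so the sponsor should also say which cut-off the programs used and rerun the Week 52 PP tables if it was Day 224.

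As a clarification only, SAP 3.8.1 and Appendix 2 could say that, in Group 1, the on-treatment cut at ART restart applies to anyone taken off the long-acting regimen and returned to oral ART, whatever the dosing-completion answer. The text should exclude temporary oral ART under protocol 5.3.2 and leave the snapshot's lack-of-efficacy failure branch unchanged.

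The cost is a few lines of SAP text and a small programming check. No new data are needed.

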3.1.4. Safety Analysis Set

The Safety Analysis Set includes all participants who were randomized and received at least 1 dose of any study drug (ie, study treatment, including LEN, GS-5423, GS-2872, or continued with their baseline ART regimen).

3.1.5. Pharmacokinetic (PK) Analysis Sets

The PK Analysis Sets include the follows:

- LEN PK Analysis Set includes all randomized participants who have received at least 1 dose of study drug, and have at least 1 nonmissing LEN concentration value reported by the PK laboratory test.
- TAB PK Analysis Set includes all randomized participants who have received at least 1 dose of study drug, and have at least 1 nonmissing GS-5423 concentration value reported by the PK laboratory test.
- ZAB PK Analysis Set includes all randomized participants who have received at least 1 dose of study drug, and have at least 1 nonmissing GS-2872 concentration value reported by the PK laboratory test.

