8.3.1.3.2. Pharmacokinetic Substudy Analysis Set

The primary analysis set for the PK substudy analyses is defined as the PK Substudy Analysis Set, which will include all randomized participants who are enrolled into the optional PK substudy, have received at least 1 dose of GS-5423, GS-2872, or LEN, and have at least 1 nonmissing PK substudy concentration value reported by the PK laboratory for corresponding analytes (eg, GS-5423, GS-2872, LEN, or metabolites, if applicable).

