9.1.4. Informed Consent

The investigator is responsible for obtaining written informed consent from each individual participating in this study after adequate explanation of the aims, methods, objectives, and potential hazards of the study before undertaking any study-related procedures. The investigator must use the most current IRB-approved ICF for documenting written informed consent. Each ICF (or assent as applicable) will be appropriately signed and dated by the participant or the participant's legally authorized representative, the person conducting the consent discussion, and an impartial witness (if required by IRB or local requirements).

The ICF will inform participants about genomic testing and/or planned sample retention. In addition to the study-specific ICF to be signed by each participant participating in the study, participants will be required to document additional consent to provide additional samples and/or to allow the use of the remainder of their already-collected specimens for optional future research, in accordance with applicable regulations. In addition to the study-specific ICF to be signed by each participant participating in the study, participants will be required to document additional consent to provide additional samples for optional genomic research. The results of the tests performed on the samples will not be given to the participant or the investigator. The stored biological samples will be destroyed no later than 15 years after the end of study or per country requirements, but participants may at any time request that their stored samples be destroyed. Additionally, participants will be required to document consent if they agree to provide samples for the optional PK substudy (see Section 6.3.6).

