8.3.2. Statistical Analysis of PK Parameters

Individual estimates of pharmacokinetic parameters of LEN, GS-5423, and GS-2872 will be listed and summarized using descriptive statistics by treatment periods (Day 0 to Week 26, and Week 26 to Week 52) (eg, sample size, arithmetic mean, coefficient of variation %, SD, 95% CI for the arithmetic mean, geometric mean, %CV, median, minimum, maximum, Q1, Q3, sample size of natural log-scale [LN], geometric mean, Geometric Coefficient of Variation [%GVC], 95% Confidence Interval for Geometric Mean [GCI], mean of LN, SD of LN).

PK parameters listed in Table 8-1 will be included in the following tables by treatment periods (as applicable).

- Individual estimates and summary statistics of plasma LEN PK parameters using the LEN PK Analysis Set
- Individual estimates and summary statistics of serum GS-5423 PK parameters using the GS-5423 PK Analysis Set
- Individual estimates and summary statistics of serum GS-2872 PK parameters using the GS-2872 PK Analysis Set

PK parameters could be unestimatable due to insufficient concentration data or may be estimated but marked for exclusion due to reasons such as the participant received an incorrect dose. In such cases, the PK parameters will be included in the listing (as not reported [NR] or the estimate values) but will be excluded from the summary statistics, with reasons for exclusion identified.

In addition, determination of half-life and corresponding correlation coefficient will be provided in the following listings by treatment periods:

- Individual data on determination of GS-5423 serum half-life and corresponding correlation coefficient using the GS-5423 PK Analysis Set
- Individual data on determination of GS-2872 serum half-life and corresponding correlation coefficient using the GS-2872 PK Analysis Set

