8.4. Changes From Protocol-Specified PK Analyses

There are no deviations from the protocol-specified PK analyses.

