- c Vital signs: blood pressure, pulse, and temperature. On dosing days for LEN + GS-5423 + GS-2872, vital signs should be recorded prior to start of study drug administration and 30 minutes (± 10 minutes) after completion of both GS-5423 and GS-2872 infusion, if coadministered or the GS-2872 infusion, if sequentially administered.
- d Refer to Table 6 for specific tests that are not on a standard chemistry panel (eg, amylase/lipase, uric acid).
- e CD4+ and CD8+ T-cell counts at post-ESDD 90-day follow-up visit only.
- f An FSH test is required for participants assigned female at birth who are younger than 54 years, have not undergone permanent sterilization, are not on hormonal contraception, and have stopped menstruating for at least 12 months but do not have documentation of ovarian hormonal failure; see Appendix 11.3.
- g Participants assigned female at birth of childbearing potential only. On dosing days, urine pregnancy test to be performed predose. A positive urine pregnancy test should be confirmed with a serum pregnancy test.
- h HIV-1 genotype and phenotype testing for participants with confirmed virologic failure and HIV-1 RNA ≥ 200 copies/mL. Refer to Section 6.3.9.2.
- i HIV reservoir sample (PBMC) and ECG to be collected at Day 1, Week 26, Week 52, Week 104, and every 12 months thereafter.

CCI

CCI

- n Serum PK samples for GS-5423 and GS-2872 will be collected in all participants as follows:
- Day 1: 0 hours (predose, ≤ 30 minutes prior to dosing of oral LEN) and within 5 minutes after the end of the second antibody infusion (GS-2872).
 - Week 26: 0 hours (predose, ≤ 30 minutes prior to dosing of SC LEN) and within 5 minutes after the end of the second antibody infusion (GS-2872).
 - Week 52 and subsequent dosing days: 0 hours (predose, ≤ 30 minutes prior to dosing of SC LEN) and within 5 minutes after the end of both antibody infusions (GS-5423 and GS-2872), if coadministered or the second antibody infusion (GS-2872), if sequentially administered.
 - A single any time sample at other scheduled visits.
- o Plasma samples for LEN will be collected in all participants as follows:
- Day 1: 0 hours (predose, ≤ 30 minutes prior to dosing of oral LEN) and within 5 minutes after the end of the second antibody infusion (GS-2872).
 - Week 26 and subsequent dosing days: 0 hours (predose, ≤ 30 minutes prior to dosing of SC LEN).
 - A single any time sample at other scheduled visits.

CCI

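### The SAP drops the protocol's PK Substudy Analysis Set without declaring it, and pools substudy and core-only profiles in the LEN Cmax/Tmax and antibody AUCtau summaries

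*SAP*

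**What the plan says.** **Protocol.** Section 8.3.1.3.2 names a PK Substudy Analysis Set, "which will include all randomized participants who are enrolled into the optional PK substudy", who also need a dose and a substudy concentration. It is the primary set for the substudy analyses. Section 9.1.4 asks for separate consent from participants "if they agree to provide samples for the optional PK substudy", so only some give the extra samples. The secondary endpoints in Section 2 include AUC, half-life, Cmax and Tmax for all three agents, as appropriate.

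**SAP.** Section 3.1.5 has three PK sets, one per analyte. The LEN set takes "all randomized participants who have received at least 1 dose of study drug, and have at least 1 nonmissing LEN concentration value"; the TAB and ZAB sets follow the same pattern. There is no substudy set and no redaction mark in that section. Table 8-1 lists, after Day 1 dosing, LEN Cmax, Cmaxday1, Tmax, Tmaxday1 and Ctrough, and antibody AUCtau, Ctrough, Cmax, half-life and Tmax. After Week 26 dosing it lists only Ctrough for LEN, and AUCtau, Ctrough, Cmax and Tmax for the antibodies. Section 8.3.2 plans "Individual estimates and summary statistics of plasma LEN PK parameters using the LEN PK Analysis Set" and does the same for each antibody. Section 8.4 states: "There are no deviations from the protocol-specified PK analyses". Section 3.7 still speaks of intensive PK samples but gives them no analysis set.

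**The concern.** Cmax and Tmax depend on when blood is drawn. If some participants are sampled densely in the first days and others only once on Day 1 and next at Week 4, a pooled summary mixes two different measurements. Part of the spread in LEN Cmax and Tmax would then reflect who consented to the substudy rather than pharmacokinetics.

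These are secondary endpoints. Protocol 1.4.2 also supports the simplified LEN loading regimen by predicting that target concentrations are reached within days, which is the period the core schedule leaves unsampled. The statement in SAP 8.4 would leave a reader of the report unaware that a set named in the protocol had been dropped.

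**Working it through.** The plan states no figure to reproduce here. The check compares the set definitions with the sampling schedule and adds up the permitted times.

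**1. Core LEN samples, Treatment Group 1** (Protocol 6.3.6.1 and 3.1.1; SAP Table 13-1): Day 1 predose, Day 1 within 5 minutes of the end of the GS-2872 infusion, then one sample at each of Weeks 4, 12 and 24, and Week 26 predose. The Day 2, 8 and 15 columns carry no mark in the core PK rows.

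**2. Time of the one Day 1 postdose sample** after the first oral LEN dose (Protocol 5.3, sequential infusions, no interruption), in minutes:

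| Step | Earliest | Latest |
|---|---|---|
| Oral to SC LEN | 0 | 30 |
| Two SC injections | 0 | 15 |
| SC LEN to GS-5423 | 0 | 60 |
| GS-5423 infusion | 30 | 30 |
| Gap | 15 | 60 |
| GS-2872 infusion | 30 | 30 |
| Infusion end to sample | 0 | 5 |
| **Total** | **75 (1.25 h)** | **230 (3.83 h)** |

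**3. Gap to the next core sample.** Week 4 is nominal Study Day 28, so 28 − 1 = 27 days after Day 1. With a window of ±3 days the gap is about 24 to 30 days; with ±6 days, about 21 to 33. The Day 2 oral dose is taken at home, and no core sample follows it before Week 4.

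**4. Consequence for LEN.** Cmaxday1 is a single value and Tmaxday1 is its clock time, 1.25 to 3.8 h by design. Overall Cmax is the largest of five postdose samples (Day 1, Weeks 4, 12 and 24, and Week 26 predose), so Tmax is either about 1 to 4 h or Week 4 or later.

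**5. Do the SAP's safeguards catch this?** Section 8.3.2 excludes from the summaries parameters that cannot be estimated for lack of data. Section 8.2.2 gives case-by-case review to AUCinf, the terminal rate constant and half-life, and to the use of nominal times for AUC. Cmax and Tmax can be read off any profile with one quantifiable sample, so neither rule removes them.

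**6. Antibodies.** Every Group 1 participant has a Day 1 sample 0 to 5 minutes after the GS-2872 infusion ends. That is 15 + 30 + 0 = 45 to 60 + 30 + 5 = 95 minutes after the GS-5423 infusion ends. Cmax is therefore little affected. AUCtau can be, because the distribution phase is unsampled until Week 4.

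An illustration, none of whose inputs is in the documents except the linear-up/log-down rule: a two-compartment model with CL 0.06–0.12 L/day, V1 3.0–3.5 L, Q 0.2–0.8 L/day and V2 1–4 L gives a Day 1 AUCtau bias of roughly +4% to +20% on core samples. Adding samples on Days 2, 8 and 15 reduces the bias to under +2%. That those are the substudy days is an inference, since the relevant rows and footnote are redacted.

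**The case against.** The strongest reply is that the protocol does not tie these parameters to the substudy set. It makes that set primary for the substudy analyses only, while Section 8.8 summarises PK parameters by treatment group as appropriate. The text just before 8.3.1.3.2, apparently the main PK set, is redacted. Deriving parameters in the full sets may therefore be what the protocol intended. This stands: the documents show that a named set was omitted without comment, not that each full-set parameter is itself a departure. The version gap does not readily explain the omission. The SAP rests on Amendment 3, and the Amendment 4 log lists no change to the analysis sets.

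Two stronger readings are tempting. A reader might infer that core samples miss the LEN peak and understate Cmax. The text gives no peak time and Figure 4 is not shown; a late peak from the SC depot could be caught at Week 4, 12 or 24. A reader might also infer that Cmax, Tmax and AUC are all compromised for every analyte. Table 8-1 has no LEN AUC, lists LEN Cmax and Tmax after Day 1 dosing only, and applies as applicable. Restricting antibody Cmax to substudy volunteers would discard usable data.

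It is also fair that the summaries are descriptive, that medians, quartiles and individual values would reveal a split in Tmax, and that the LEN target in Protocol 1.4.2 is a trough criterion. These points limit the harm, but they leave the pooled means and intervals hard to interpret.

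**Conclusion.** The point holds in a limited form. SAP 3.1.5 omits a set the protocol defines, SAP 8.4 reports no deviation, and SAP 8.3.2 pools substudy and core-only participants. For core-only participants nothing is sampled between about 4 h (at most 3.83 h) after the first oral LEN dose and Week 4. Their Tmaxday1 therefore carries no pharmacokinetic information, and their Cmax cannot reflect any peak in that gap.

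The direction and size of any effect on pooled LEN Cmax cannot be determined, because the LEN peak time, substudy size and substudy sampling times are not shown. The antibody AUCtau range is illustrative and depends on assumed parameters. The timing result assumes sequential infusions within the permitted intervals. Trough summaries and the virologic endpoints are not affected.

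**What to change.** - **SAP 3.1.5:** restore the PK Substudy Analysis Set as the protocol defines it.
- **SAP Table 8-1 and 8.3.2:** summarise LEN Cmax, Tmax, Cmaxday1 and Tmaxday1, and noncompartmental Day 1 antibody AUCtau and half-life, in that set. Show core-only profiles separately and do not pool the two.
- **Keep in the full LEN, TAB and ZAB PK sets:** trough concentrations and antibody end-of-infusion Cmax.
- **SAP 8.4:** replace the statement of no deviations with one that says how the substudy data are handled.

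The cost is SAP wording and table populations; no new data are needed. The downside is a smaller n, of unknown size, for the substudy-only summaries.
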